6.2. Spirometry

Pre-bronchodilator FEV₁, FVC, and FEF_{25%-75%} and post-bronchodilator FEV₁ will be measured using spirometry. The FEV₁ is the volume of air which can be forcibly exhaled from the lungs in the first second, measured in liters. The FVC is the volume of air that can be forcibly blown out after full inspiration, measured in liters. The FEF_{25%-75%} is the forced expiratory flow at 25% to 75% forced vital capacity. For post-bronchodilatory spirometry, SABAs, such as salbutamol or albuterol, administered via a metered dose inhaler should be used. Four separate doses (eg, albuterol 360 μ g or salbutamol 100 μ g ex-valve) should be given by metered dose inhaler, as tolerated. Post-bronchodilator spirometry should be completed a minimum of 15 minutes after dosing of SABA. Spirometry will be done according to American Thoracic Society/European Respiratory Society 2005 procedural guidelines. The National Health and Nutrition Survey III reference equations will be used.

6.3. Asthma Control Questionnaire

The ACQ-6 is a validated asthma assessment tool that has been widely used ([Juniper et al 1999](#)). Six questions are self-assessments (completed by the patient). Each item on the ACQ-6 has a possible score ranging from 0 to 6, and the total score is the mean of all responses ([Appendix A](#)).

6.4. Asthma Quality of Life Questionnaire for Patients 12 years and Older

The AQLQ+12 is a modified version of the standardized AQLQ, which was developed to measure functional impairments experienced by adults ≥ 17 years of age. The AQLQ+12 is valid for patients aged 12 to 70 years and includes 32 questions in 4 domains (symptoms, activity limitation, emotional function, and environmental stimuli) ([Juniper et al 1992](#), [Wyrwich et al 2011](#)). Patients are asked to recall their experiences during the previous 2 weeks and score each of the questions on a 7-point scale where 7 = no impairment and 1 = severe impairment ([Appendix B](#)).

7. ASSESSMENT OF SAFETY

In this study, safety will be assessed by qualified study staff by evaluating the following:

- Adverse events throughout the study
- Clinical laboratory test results (serum chemistry, hematology, and urinalysis) throughout the study
- Vital signs (pulse, respiratory rate, body temperature, blood pressure, and SpO₂) throughout the study
- Physical examination findings throughout the study
- Concomitant medication usage throughout the study

7.1. Adverse Events

7.1.1. Definition of an Adverse Event

An adverse event is any untoward medical occurrence in a patient administered a pharmaceutical product, regardless of whether it has a causal relationship with this treatment.

In this study, any adverse event occurring after the clinical study patient has signed the informed consent form should be recorded and reported as an adverse event.

An adverse event can, therefore, be any unfavorable and unintended physical sign, symptom, or laboratory parameter that develops or worsens in severity during the course of this study, or significant worsening of the disease under study, or of any concurrent disease, whether or not considered related to the study drug. A new condition or the worsening of a pre-existing condition will be considered an adverse event. Stable chronic conditions (such as arthritis) that are present before study entry and do not worsen during this study will not be considered adverse events.

Accordingly, an adverse event can include any of the following:

- intercurrent illnesses
- physical injuries
- events possibly related to concomitant medication
- significant worsening (change in nature, severity, or frequency) of the disease under study or other pre-existing conditions (Note: A condition recorded as pre-existing that is intermittently symptomatic [eg, headache] and that occurs during this study should be recorded as an adverse event.)
- drug interactions
- laboratory or diagnostic test abnormalities that result in the withdrawal of the patient from the study, are associated with clinical signs and symptoms or a serious adverse event, require medical treatment or further diagnostic work up, or are considered by the investigator to be clinically significant (Note: Abnormal laboratory test results at

the screening visit that preclude a patient from entering the study or receiving study treatment are not considered adverse events.)

Worsening of the disease under study (ie, asthma) including asthma exacerbations requiring additional controller medication, will be collected as an efficacy assessment in this study. The aforementioned worsening of asthma should be recorded as an adverse event only if the presentation or outcome is more severe than would typically be expected from the normal course of the disease in a particular patient.

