The most common preferred terms (reported in >5% of patients in the reslizumab 3.0 mg/kg group) were asthma (232 [23%] and 289 [40%] patients in the reslizumab 3.0 mg/kg and placebo groups, respectively), nasopharyngitis (103 [10%] and 103 [14%] patients, respectively), upper respiratory tract infection (96 [9%] and 69 [10%] patients, respectively), headache (78 [8%] and 62 [9%] patients, respectively), and sinusitis (57 [6%] and 51 [7%] patients, respectively).

The incidence of all common adverse events (>2%) was the same or higher in the placebo group compared to the reslizumab group with the exception of oropharyngeal pain, which was slightly higher in the 3.0 mg/kg reslizumab-treated patients (2.6%) than in the placebo-treated patients (2.2%).

Serious Adverse Events

The incidence of serious adverse events was similar in the reslizumab 3.0 mg/kg treatment group (6%) compared with the placebo treatment group (9%). The serious adverse event reported with the highest incidence was asthma (preferred terms of asthma, asthma crisis, and status asthmaticus), reported by 24 (3%) patients in the placebo group and 24 (2%) patients in the reslizumab 3.0 mg/kg group. Three serious adverse events of anaphylaxis events were assessed as related to reslizumab treatment.

Deaths

There were 4 deaths in the Phase 3 asthma clinical development program: 1 death occurred in a placebo-treated patient and 3 deaths occurred in the ongoing open-label study (Study C38072/3085). None of the deaths were considered related to reslizumab.

Laboratory Findings

Overall, laboratory test values were similar in patients treated with reslizumab and placebo, with the exception of creatine phosphokinase (CPK) elevation and the expected pharmacological effect of decreasing blood eosinophil counts. There were no clinically meaningful differences or potentially clinically important trends in vital signs, electrocardiogram (ECG) intervals, or overall ECG assessments.

Adverse Drug Reactions

Anaphylaxis

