3.12. Stopping Rules and Discontinuation Criteria

Other than in the event a participant becomes pregnant, there are no formal rules for early termination of this study. During the conduct of the study, serious adverse events will be reviewed by Teva in an ongoing basis (see Section 7.1.5) as they are reported to Teva by the investigational center to identify safety concerns.

The study may be terminated by the sponsor for reasons including, but not limited to, a safety concern.

Termination of patient participation is required in Part 2 in the event of an asthma exacerbation. Should this happen, additional patients will be enrolled until 10 patients (including at least 4 female patients) have completed all 3 post-reslizumab/placebo PET/CT scans.

A patient may discontinue participation in the study at any time for any reason (eg, lack of efficacy, withdrawal of consent, and adverse event); every effort should be undertaken to find out the reason for discontinuation. The investigator or sponsor can withdraw a patient from the

study at any time for any reason (eg, protocol violation or deviation as defined in Section [11.1.2](#), noncompliance, or adverse event).

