7.1.8. Withdrawal Due to an Adverse Event

Any patient who experiences an adverse event may be withdrawn from the study or from study treatment at any time at the discretion of the investigator. If a patient is withdrawn wholly or in part because of an adverse event, both the adverse events page and termination page of the CRF will be completed at that time.

The patient will be monitored at the discretion of the investigator (eg, until the event has resolved or stabilized, until the patient is referred to the care of a health care professional, or until a determination of a cause unrelated to the study drug or study procedure is made). The investigator must inform the Sponsor’s Authorized Representative as soon as possible of each patient who is being considered for withdrawal due to adverse events. Additional reports must be provided when requested.

If a patient is withdrawn from study for multiple reasons that include adverse events, the termination page of the CRF should indicate that the withdrawal was related to an adverse event. An exception to this requirement will be the occurrence of an adverse event that in the opinion of the investigator is not severe enough to warrant discontinuation but that requires the use of a prohibited medication, thereby requiring discontinuation of the patient. In such a case, the reason for discontinuation would be need to take a prohibited medication, not the adverse event.

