### **8.2. Adverse Events**

All adverse events will be coded using the latest available version of the Medical Dictionary for Regulatory Activities (MedDRA), associated with five levels of classifications: a System Organ Class (SOC), a High Level Group Term (HLGT), a High Level Term (HLT), a Preferred Term (PT) and a lowest Level Term (LLT).

Only Treatment Emergent Adverse Event (TEAE), defined as events occurring after the first drug administration and until the end of the study, will be presented, based on Safety analysis set.

Similarly, AEs occurring between ICF signing and end of Part 1 will be presented based on Enrolled analysis set.

In the AE summary tables each patient will be counted only once in each preferred term or system organ class category for the analyses of safety. Summaries will be presented for all adverse events by treatment group, and overall as following:

- All AEs sorted by SOC and PT based on Safety analysis set (Summary 15.3.1.1) and on Enrolled analysis set (Summary 15.3.1.2)
- All AEs sorted by PT based on Safety analysis set (Summary 15.3.1.3) and on Enrolled analysis set (Summary 15.3.1.4)
- Treatment-related AE sorted by SOC and PT based on Safety analysis set (Summary 15.3.1.5)
- Serious AE sorted by SOC and PT based on Safety analysis set (Summary 15.3.1.6)
- Non serious AE sorted by SOC and PT based on Safety analysis set (Summary 15.3.1.7)
- AE sorted by SOC, PT and severity based on Safety analysis set (Summary 15.3.1.8).

Asthma deterioration will be descriptively summarized for safety analysis set (Summary 15.3.1.9).

Patient listings of serious adverse events and adverse events leading to withdrawal will be presented. Suspected anaphylaxis/hypersensitivity and CPK reactions will be listed individually (Listings 16.2.8.12 and 16.2.8.13).

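### Asthma exacerbations judged typical for a patient are excluded from adverse events and sent to an efficacy assessment found nowhere in the plan, so serious or terminating ones can miss the AE and SAE outputs

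*Protocol*

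**What the plan says.** Protocol 7.1.1 defines an adverse event broadly. Both the definition and the list below it include worsening of the trial disease; the list has "significant worsening (change in nature, severity, or frequency) of the disease under study". The last paragraph of the section treats asthma differently: "Worsening of the disease under study (ie, asthma) including asthma exacerbations requiring additional controller medication, will be collected as an efficacy assessment in this study". It adds that such worsening "should be recorded as an adverse event only if the presentation or outcome is more severe than would typically be expected" in the individual patient.

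Other provisions that bear on this:

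- **Protocol 7.1.5.1** defines a serious adverse event as an adverse event with one of the listed outcomes. Protocol 7.1.5.3.1 attaches the 24-hour report to serious adverse events.
- **Protocol 3.12**: "Termination of patient participation is required in Part 2 in the event of an asthma exacerbation". Further patients are then enrolled until 10 have completed all three post-dose scans.
- **SAP 8.2** builds the AE tables and the SAE and AE-withdrawal listings from adverse events. It adds one line: "Asthma deterioration will be descriptively summarized for safety analysis set (Summary 15.3.1.9").
- **SAP 5.2** summarises withdrawals by reason, and **SAP 8.8** summarises concomitant medications.

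**The concern.** Taking disease worsening out of AE recording is workable only if another data stream reliably captures the same events. Here the stream is named but not specified, and the exclusion turns on a patient-by-patient judgement of what is typical. Two similar exacerbations could be recorded differently because the patients' histories differ.

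The filter also sits ahead of the safety oversight. There is no data monitoring committee (Protocol 3.8.3). Ongoing oversight consists of sponsor review of reported SAEs (3.12) and periodic review of AEs (7.9), and both see only what has been recorded as an AE. The population may include patients for whom severe episodes are not unusual: SAP 5.4 tabulates earlier asthma hospitalisation or emergency visits, intensive care admission and intubation.

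The events matter for reading the trial as well. A patient with a Part 2 exacerbation leaves the study, GLG is not imputed (SAP 4.3), and a patient who leaves before any post-baseline efficacy assessment is outside the full analysis set. The AE and withdrawal records are then a main account of what happened to that patient.

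**Working it through.** **1. Is there an efficacy assessment that covers exacerbations?** I looked in each place where one should appear.

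| Place | Content | Exacerbation? |
|---|---|---|
| Protocol 2.3.1 to 2.3.3, 9.5.1 to 9.5.3 | GLG, LP SUVmean; blood eosinophils, FEV1, FeNO, AQLQ; biomarkers, other lung function, nodal and marrow FDG, sputum eosinophils | No |
| Protocol 3.3 and 3.6 (efficacy measures) | Same variables | No |
| Protocol Table 2, SAP Table 1 (schedules) | No row for exacerbation or worsening | No |
| Protocol Section 6 (methods) | PET/CT, spirometry, ACQ, AQLQ | No |
| SAP Section 6 (efficacy analyses) | Same endpoints | No |

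**2. Does seriousness bring a typical exacerbation back in?** Under 7.1.1, an episode that is not worse than the patient's expected course is not an AE. Under 7.1.5.1, an SAE is a kind of AE. Neither section says that meeting a seriousness criterion overrides the 7.1.1 exclusion. Read literally, an admission judged usual for that patient is not an AE, therefore not an SAE, and the 24-hour report is not triggered.

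**3. Does forced termination bring it back in?** Protocol 3.12 ends participation but says nothing about AE status. If the event was never recorded as an AE, the AE-withdrawal listing has nothing to show.

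**4. The programme figures.** Inputs are from Protocol 1.3.2.2. The denominators, 1028 and 730, are those given there for the myalgia counts; I assume they also apply to asthma.

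- Asthma AE: 232/1028 = 22.6% (stated 23%); 289/730 = 39.6% (stated 40%).
- Next most frequent term, nasopharyngitis: 103/1028 = 10.0%; 103/730 = 14.1%.
- Asthma SAE: 24/1028 = 2.3% (stated 2%); 24/730 = 3.3% (stated 3%).

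The stated figures reproduce, and asthma was clearly the commonest AE as well as the most frequent SAE.

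**5. What might be expected here (illustration only).** The programme figures come from dosing every 4 weeks for up to 52 weeks. Assume a constant hazard, 7 weeks of observation and 5 patients per arm, and rescale with p7 = 1 − (1 − p)^(7/T), where p is the programme incidence and T the follow-up in weeks.

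| T | Reslizumab p7 | Placebo p7 | Patients expected of 10 | P(at least one) |
|---|---|---|---|---|
| 52 | 3.4% | 6.6% | 5(0.034) + 5(0.066) = 0.5 | 40% |
| 16 | 10.6% | 19.8% | 5(0.106) + 5(0.198) = 1.5 | 81% |

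Here P(at least one) = 1 − (1 − p7,res)^5 × (1 − p7,pbo)^5. This is the chance that some asthma AE arises, not the chance that one goes unrecorded; the documents give no basis for the latter.

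**6. Size of one omission.** 1/5 = 20 percentage points in an arm. If that arm has one extra patient enrolled under 3.12, it is 1/6, about 17 points.

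**The case against.** The strongest reply is that 7.1.1 is a general rule followed by a specific exception, not a contradiction, and that episodes worse than expected remain AEs. That is a fair reading of the structure, and it rules out saying that exacerbations as a class are removed from AE recording. It does not supply the missing efficacy assessment, nor does it say what happens to a typical but serious episode.

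A second reply is that few investigators would call a hospital admission a patient's normal course, and that 7.1.5.1 gives emergency treatment of allergic bronchospasm as an example of an important medical event. In practice most such cases would probably be reported. The gap is a possible omission under the text, not a certain one.

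A third reply is that traces exist elsewhere: Summary 15.3.1.9, disposition by reason and concomitant medications. With so few patients these can be read case by case, and the CRF, which is not among the documents, may contain a collection page. This stands in part. However, disposition and medication tables do not give the event's severity, seriousness or outcome, and Summary 15.3.1.9 has no definition and no named source.

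Two stronger readings are tempting and should not be drawn:

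- *Exacerbation is the only event that ends participation.* It is not: pregnancy (7.4.2.1) and a broken blind (3.8.2) also require withdrawal.
- *Protocol 7.1.8 would recode these withdrawals, because "the reason for discontinuation would be need to take a prohibited medication, not the adverse event".* That exception covers only an AE judged not severe enough to warrant stopping. It fits poorly with an exacerbation that requires termination under 3.12, and for multiple reasons that include an AE the default in 7.1.8 is to record the withdrawal as AE-related.

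The Part 1 argument is also limited. No study drug is given then, Part 1 AEs are tabulated, and reasons for screen failure and non-randomisation are summarised.

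**Conclusion.** The point holds in a bounded form. The rule excludes expected-course exacerbations from AEs and assigns them to an efficacy assessment that neither document specifies. As nothing makes seriousness override that exclusion, a serious or terminating exacerbation can be absent from the AE and SAE outputs, the AE-withdrawal listing and expedited reporting.

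This rests on reading the text as written and on the absence of any collection instruction in the two documents; a CRF page could reduce the practical loss but would not repair the SAE definition. The frequency in this trial is uncertain: step 5 spans 0.5 to 1.5 patients of 10 under assumptions the documents do not directly support, and it counts every asthma AE, not only those at risk of exclusion. The trial is descriptive and plans no comparison with programme data, so the harm lies in incomplete safety recording and reporting, not in a biased test. The matter should be corrected.

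**What to change.** **Protocol 7.1.1.** Delete the two sentences on asthma worsening, or at minimum remove the efficacy label. State that:

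- any exacerbation that needs treatment beyond increased SABA use (the threshold Section 3.1 already applies to screening), or that leads to termination, is recorded as an AE; and
- any event that meets a 7.1.5.1 criterion is an SAE, whatever is usual for the patient.

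**SAP 8.2.** Define asthma deterioration as these same events, name the CRF page that supplies them, and show them on a separate row, so that the remaining AEs can still be read without them. A matching Part 1 summary is optional. Section 7.1.8 needs no change.

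**Cost.** Protocol and SAP wording plus a CRF instruction. AE counts will rise and will include events that also reflect lack of efficacy, which the separate row makes visible. The change governs recording only and alters no treatment or stopping rule.

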7.1.2. Recording and Reporting of Adverse Events

For adverse event recording, the study period is defined for each patient as that time period from signature of the Informed Consent Form through the end of the follow up period. For this study, the follow up period is defined as 1 week after visit 6 (week 6), approximately 7 weeks after the single dose of reslizumab. Adverse events will be collected at each visit, including the follow-up visit, via adverse event inquiry.

All adverse events that occur during the defined study period must be recorded on the source documentation and transcribed to the CRF, regardless of the severity or seriousness of the event or judged relationship to the study drug. For serious adverse events, the Serious Adverse Event Form must be completed and the serious adverse event must be reported immediately (see Section 7.1.5.3.1). The investigator does not need to actively monitor patients for adverse events once the study has ended. Serious adverse events occurring in a patient after the end of the study should be reported to the sponsor if the investigator becomes aware of them, following the procedures described in Section 7.1.5.3.1.

At each contact with the patient, the investigator or designee must question the patient about adverse events by asking an open-ended question such as “Have you had any unusual symptoms or medical problems since the last visit? If yes, please describe”. All reported or observed signs and symptoms will be recorded individually, except when considered manifestations of a medical condition or disease state. A precise diagnosis will be recorded whenever possible. When such a diagnosis is made, all related signs, symptoms, and any test findings will be recorded collectively as a single diagnosis on the CRF and, if it is a serious adverse event, on the Serious Adverse Event Form.

The clinical course of each adverse event will be monitored at suitable intervals until resolved, stabilized, or returned to baseline; or until the patient is referred for continued care to a health care professional; or until a determination of a cause unrelated to the study drug or study procedure is made.

The onset and end dates, duration (in case of adverse event duration of less than 24 hours), action taken regarding study drug, treatment administered, and outcome for each adverse event must be recorded on the source documentation and transcribed to the CRF. The approximate time of onset for each adverse event that starts within 24 hours of study drug administration will be also recorded.

The relationship of each adverse event to study drug and study procedures, and the severity and seriousness of each adverse event, as judged by the investigator, must be recorded as described below.

7.1.3. Severity of an Adverse Event

The severity of each adverse event must be recorded as 1 of the choices on the following scale:

Mild: No limitation of usual activities

Moderate: Some limitation of usual activities

Severe: Inability to carry out usual activities

7.1.4. Relationship of an Adverse Event to the Study Drug

The relationship of an adverse event to the study drug is characterized as follows:

Term	Definition	Clarification
No reasonable possibility (not related)	This category applies to adverse events that, after careful consideration, are clearly due to extraneous causes (disease, environment, etc) or to adverse events that, after careful medical consideration at the time they are evaluated, are judged to be unrelated to the study drug.	
The relationship of an adverse event may be considered “no reasonable possibility” if it is clearly due to extraneous causes or if at least 2 of the following apply:
 
 • It does not follow a reasonable temporal sequence from the administration of the study drug. • It could readily have been produced by the patient’s clinical state, environmental or toxic factors, or other modes of therapy administered to the patient. • It does not follow a known pattern of response to the study drug. • It does not reappear or worsen when the study drug is re-administered.
Reasonable possibility (related)	This category applies to adverse events for which, after careful medical consideration at the time they are evaluated, a connection with the study drug administration cannot be ruled out with certainty.	
The relationship of an adverse event may be considered “reasonable possibility” if at least 2 of the following apply:
 
 • It follows a reasonable temporal sequence from administration of the study drug. • It cannot be reasonably explained by the known characteristics of the patient’s clinical state, environmental or toxic factors, or other modes of therapy administered to the patient. • It disappears or decreases on cessation or reduction in dose. There are important exceptions when an adverse event does not disappear after discontinuation of the study drug, yet a drug relationship clearly exists. • It follows a known pattern of response to the study drug.

